2.1.7 Ublituximab

Ublituximab (TG-1101) is a glycolengineered chimeric monoclonal antibody engineered to optimally target the human CD20 antigen. Ublituximab targeting of CD20 promotes antibody-dependent cell-mediated cytotoxicity (ADCC) of cells expressing this protein. Notably, ublituximab has a high affinity for Fc γ RIIIa (CD16) receptors, which is associated with eliciting greater ADCC than targeting by the other CD20 antibodies [43, 44]. Ublituximab targeting of CD20 is also associated with classical activation of the complement pathway (CDC), as well as induction of B-cell apoptosis.

Excluding the three Phase III studies that are being conducted under SPA (UTX-TGR-304, TG1101-RMS301, and TG1101-RMS302) and the three Phase II extension studies (UTX-TGR-204, UTX-TGR-501, and TG1101-RMS201E), as of 10 May 2019, over 1020 subjects have been exposed to ublituximab through ten Phase I or II clinical trials and one Phase III clinical trial (three of which are still enrolling).

Ublituximab exposure in oncology has ranged in dose from 450 mg to 1200 mg, both as induction (weekly infusions x 4 or 6 weeks) and maintenance (monthly through month 6 followed by quarterly). The maximum tolerated dose/exposure has not been established however the Phase II and III dose in oncology settings has been selected at 900 mg/infusion.

In oncology, the following adverse reactions have been observed: Infusion-related reaction was the most frequent drug-related AE in all studies, typically occurring during the first ublituximab infusion. Grade 3-4 neutropenia, rarely associated with a febrile episode, has been reported and usually resolved either spontaneously or in a few days with G-CSF therapy for oncology. Drug-related Grade 3 thrombocytopenia and worsening from slight to Grade 3-4 pancytopenia has also been reported although minimal. Asymptomatic, isolated, and transient Grade 2-3 drug-related elevated liver enzymes have been observed as well. Most subjects who experience ublituximab related adverse events may have a dose interruption or delay, and usually resume at the original dose.

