7.0 DOSE DELAY / MODIFICATION GUIDELINES

7.1 Dose Delays/ Modification

- Toxicities will be graded using the NCI CTCAE v 5.0.
- Baseline values are from the last values obtained prior to treatment.
- Both acalabrutinib and umbralisib may be dose reduced for toxicity. If a toxicity occurs, both drugs (as well as ublituximab) may be interrupted until resolution to Grade 1, to baseline, or as noted in Table 7.1.1. Following that, either or both oral agents may be dose reduced based on suspected attribution. General guidelines for recommended dose delays and modifications are provided below.
- No reduction in the dose of ublituximab is permitted. If Grade 4 anaphylaxis is observed at any point during ublituximab treatment, permanently discontinue ublituximab treatment and intervene as per investigator discretion.
- All study drugs may be delayed for a maximum of 8 weeks to allow recovery of toxicities as specified in the tables below.
- If one of the study drugs is discontinued for toxicity, patient may continue therapy with the other study drugs.
- When treatment interruption is required for toxicity, all drugs are held. If ublituximab is suspected to be the primary reason for a recurrent toxic event, it may be discontinued only in consultation with the Study PI.

Table 7.1.1 Recommended Dose Modifications

NCI-CTCAE Grade	Dose Delay and/or Modification
Hematologic Adverse Event	
Neutropenia	
Grade \leq 2 neutropenia	Provide supportive care as warranted. Maintain current dose and schedule of acalabrutinib. Maintain current dose of umbralisib. If applicable, maintain full dose and schedule of ublituximab.
Grade 3 neutropenia	Provide supportive care as warranted. Maintain current dose and schedule of acalabrutinib. Maintain current dose of umbralisib. For recurrent or persistent Grade 3 neutropenia unresponsive to maximum supportive care:

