	
 • If toxicity is suspected to be related to umbralisib by the investigator (e. g. based on timing of toxicity occurrence during the cycle), reduce umbralisib to next lower dose level. If the lowest dose level of umbralisib is reached, reduce acalabrutinib to the next lower dose level. • If toxicity is suspected to be related to acalabrutinib by the investigator (e. g. based on timing of toxicity occurrence during the cycle), reduce acalabrutinib to the next lower dose level. For recurrences, umbralisib may be dose reduced. 
If applicable, maintain full dose and schedule of ublituximab.

Grade 4 neutropenia or occurrence of neutropenic fever or infection	
Provide supportive care as warranted.
 
 • If toxicity is suspected to be related to umbralisib by the investigator (e. g. based on timing of toxicity occurrence during the cycle): 
1st occurrence:
 
 - Delay umbralisib until Grade \leq 1 or baseline and, if present, neutropenic fever or infection is resolved; thereafter, resume umbralisib at current dose. - If grade 4 neutropenia lasts longer than 7 days (despite holding umbralisib), interrupt acalabrutinib until Grade \leq 1 or baseline and, if present, neutropenic fever or infection is resolved; thereafter, resume acalabrutinib at current dose level. 
2nd occurrence (despite maximum supportive care):
 
 - Same as for 1st occurrence, but resume umbralisib at next lower dose level (dose reduction). 
3rd occurrence (despite maximum supportive care):
 
 - Delay umbralisib and acalabrutinib until Grade \leq 1 or baseline and, if present, neutropenic fever or infection is resolved; thereafter, resume umbralisib and acalabrutinib at next lower dose level. 
4th occurrence (despite maximum supportive care):
 
 - Discontinue umbralisib. - If grade 4 neutropenia lasts longer than 7 days (despite umbralisib discontinuation), discontinue acalabrutinib. 
If applicable, delay ublituximab until Grade \leq 3 and, if present, neutropenic fever or infection is resolved; thereafter, resume ublituximab at full dose and schedule.

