	
• If toxicity is suspected to be related to acalabrutinib by the investigator (e. g. based on timing of toxicity occurrence during the cycle), delay acalabrutinib until Grade \leq 1 or baseline, thereafter, resume acalabrutinib at current dose level. For recurrences, acalabrutinib and/or umbralisib may be dose reduced. 
If applicable, delay ublituximab until Grade \leq 3 and, if present, neutropenic fever or infection is resolved; thereafter, resume ublituximab at full dose and schedule.

Thrombocytopenia	
Grade \leq 3 thrombocytopenia	
Provide supportive care as warranted.
 
Maintain current dose and schedule of acalabrutinib.
 
Maintain current dose of umbralisib.
 
If applicable, maintain full dose and schedule of ublituximab.

Grade 3 thrombocytopenia with bleeding, or Grade 4 thrombocytopenia	
Provide supportive care as warranted.
 
• If toxicity is suspected to be related to umbralisib by the investigator (e. g. based on timing of toxicity occurrence during the cycle):
1st occurrence:
- Delay acalabrutinib and umbralisib until Grade \leq 1 or baseline; thereafter, resume both acalabrutinib and umbralisib at current dose level.2nd occurrence:
- Same as for 1st occurrence, but resume umbralisib at next lower dose level (dose reduction).3rd occurrence:
- Same as for 1st occurrence, but resume both umbralisib and acalabrutinib at next lower dose level (dose reduction).4th occurrence:
- Discontinue both acalabrutinib and umbralisib. 
Delay ublituximab until Grade \leq 3; thereafter, resume ublituximab at full dose and schedule.

	
 • If toxicity is suspected to be related to acalabrutinib by the investigator (e. g. based on timing of toxicity occurrence during the cycle), delay acalabrutinib until Grade ≤ 1 or baseline, thereafter, resume acalabrutinib at current dose level. For recurrences, acalabrutinib and/or umbralisib may be dose reduced. 
Delay ublituximab until Grade ≤ 3; thereafter, resume ublituximab at full dose and schedule.

--	---

Pulmonary toxicity (pneumonitis) & Related Infections*	

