*** For patients with a prior history of hepatitis B and for those with a positive anti-HBc with negative HBsAg at screening who experience an increase in liver enzymes while on study, hold ublituximab immediately and assess for active hepatitis B infection. If negative for hepatitis B, ublituximab may be resumed. If reactivation of hepatitis B is confirmed, institute hepatitis B antiviral treatment.

Ublituximab may be resumed at investigator discretion once hepatitis B infection has resolved, with continued monitoring.

All Other Non-Hematological Adverse Events	
Grade ≤2	
Provide supportive care as warranted.
 
Maintain current dose and schedule of acalabrutinib.
 
Maintain current dose of umbralisib.
 
If applicable, maintain full dose and schedule of ublituximab.

Grade ≥3	
Provide supportive care as warranted.
 
1st occurrence:
 
 - Delay acalabrutinib and umbralisib until Grade ≤ 1 or baseline; thereafter, resume both acalabrutinib and umbralisib at current dose level. 
2nd occurrence (despite supportive care):
 
 - Same as for 1st occurrence, but resume umbralisib at next lower dose level (dose reduction). Investigator discretion may be used to maintain current dose of umbralisib if toxicity appears to be attributable to acalabrutinib. 
3rd occurrence (despite supportive care):
 
 - Same as for 1st occurrence, but resume both umbralisib and acalabrutinib at next lower dose level (dose reduction for both). If toxicity appears to be attributable specifically to umbralisib or acalabrutinib, investigator discretion may be used to maintain the current dose of umbralisib or acalabrutinib while reducing the dose of the other agent by one dose level based on attribution. 
4th occurrence (despite supportive care):
 
 - Discontinue both acalabrutinib and umbralisib. 
Delay ublituximab until ≤ grade 1; thereafter, resume ublituximab at full dose and schedule.

Umbralisib and acalabrutinib Dose Reduction Recommendations

Study Drug	Starting Dose	1 st Dose Reduction	2 nd Dose Reduction
Umbralisib (once daily, and according to schedule)	800 mg	600 mg	400 mg

Acalabrutinib	100 mg PO BID	100 mg PO once daily (QD)	N/A

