
 • A maximum of two dose level reductions are allowed for umbralisib. • If a subject requires a dose reduction of umbralisib (or acalabrutinib) due to study drug related toxicity, the dose may not be re-escalated. If further evaluation of the toxicity reveals the event was not related to umbralisib (or acalabrutinib), this should be recorded in the medical record and dose re-escalation to the previous dose may be considered in consultation with the Study PI. • If a subject: 1/ is already at the lowest dose level of umbralisib (or acalabrutinib) following prior dose reduction(s) due to study drug related toxicity, and 2/ experiences a different toxicity that would require a dose reduction, then, in consultation with Study PI, umbralisib (or acalabrutinib) may be delayed and then resumed at the same dose level when the toxicity resolves as indicated in the table for that particular toxicity. • In case of concurrent toxicities, follow the more stringent dose modification recommendations. 			

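### In Table 7.1.1, the ublituximab delay for Grade 3 thrombocytopenia with a Grade 1-2 bleed has, read literally, no length and no bleeding condition

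*Combined protocol and SAP*

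**What the plan says.** The row for "Grade 3 thrombocytopenia with bleeding, or Grade 4 thrombocytopenia" has two triggers and does not grade the bleed. It splits by whether the investigator suspects umbralisib or acalabrutinib. Both branches end with the same ublituximab instruction: "Delay ublituximab until Grade \leq 3; thereafter, resume ublituximab at full dose and schedule". The oral agents in the row wait for Grade 1 or lower, or baseline. The row directly above it, for thrombocytopenia of Grade 3 or lower, keeps all three drugs going.

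The Grade 4 neutropenia row uses the same Grade 3 threshold for ublituximab but adds a second condition: "if present, neutropenic fever or infection is resolved; thereafter, resume ublituximab at full dose and schedule".

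Three general statements in Section 7.1 also bear on this:

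- Interruption: "both drugs (as well as ublituximab) may be interrupted until resolution to Grade 1, to baseline, or as noted in Table 7.1.1".
- Scope of a hold: "When treatment interruption is required for toxicity, all drugs are held".
- Closing notes to the table: "In case of concurrent toxicities, follow the more stringent dose modification recommendations".

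For other non-hematological events of Grade 3 or higher, the table says "Delay ublituximab until ≤ grade 1; thereafter, resume ublituximab at full dose and schedule". For those of Grade 2 or lower, it maintains ublituximab. Section 7.1 presents the table as general, recommended guidance.

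**The concern.** At Grade 3, bleeding is what moves a patient from the row that continues treatment to the row that interrupts it. Yet the ublituximab line in the second row takes no account of the bleeding. A site could follow the general hold and wait for Grade 1 or baseline. It could equally follow the table line and infuse on schedule. Either site could cite the protocol.

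Holding the antibody here has a purpose. Section 2.1.7 says of ublituximab: "Drug-related Grade 3 thrombocytopenia and worsening from slight to Grade 3-4 pancytopenia has also been reported although minimal". Section 6.1 lists thrombocytopenia among the very common events with single-agent ublituximab. Table 6.2.3 warns of serious and fatal hemorrhage with acalabrutinib, which is given alongside it. What is at stake is a safety instruction for a small group of patients, not a statistical quantity.

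**Working it through.** The plan states no figure on this point, so there is none to reproduce. The check walks each entry condition through the text. It assumes that a bleed is graded under the table's row for other non-hematological events.

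| Presentation | Ublituximab line in the row | Other table text | Result |
|---|---|---|---|
| Grade 4 platelets | Not met at onset | None needed | Real delay |
| Grade 3 platelets, bleed Grade 3 or higher | Met at onset | Non-hematological row waits for Grade 1 or lower; the more stringent recommendation applies | Real delay |
| Grade 3 platelets, bleed Grade 1-2 | Met at onset, whether the grade means platelets or bleed | Non-hematological row maintains ublituximab, so it adds nothing | Zero-length delay |

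**Comparison with neutropenia.** That row has the same form: a Grade 4 cytopenia, or a clinical complication. It has the same Grade 3 threshold. Where only the complication is present, the grade condition may also be met at onset, but the resolution clause still produces a delay. The thrombocytopenia row has no such clause.

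**General text.** One bullet holds all drugs when interruption is required. The other uses permissive wording and allows the table to set the release level. Neither says which governs.

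**Oral agents.** Their criterion (Grade 1 or lower, or baseline) normally gives a real delay. It too names no bleeding condition, and it is met at onset if baseline is already Grade 3. Section 3.1 admits patients with marrow involvement at platelets down to 30,000/mm3. The documents do not print the grade cut-offs, so this is stated conditionally.

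**Illustration of size only.** These are scenarios, not bounds or estimates.

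- Patients: maximum accrual 27 (Section 12.3).
- Grade 3 or higher thrombocytopenia: 52/1079 on acalabrutinib monotherapy (Table 6.2.1). 27 × 52/1079 = 1.30. This includes Grade 4 cases, for which the rule works, and it comes from one drug of the three.
- Grade 1-2 bleeding, low case: it occurs at the pooled rate, independently of platelets. (158 − 26)/1079 = 132/1079 = 0.122.
- Grade 1-2 bleeding, high case: every such patient bleeds, and 132/158 = 0.835 of bleeds are Grade 1-2.
- Infusion due during a 7-day episode (assumed length, one episode per patient), from the 17 infusions in Section 5.3. Uniform onset over Days 2-700: 16 × 7/699 = 112/699 = 0.160. All onsets in Cycle 1, Days 2-28: (7 + 7 + 6)/27 = 20/27 = 0.741.

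| Expected patients, 7-day episode | Uniform onset | All onsets in Cycle 1 |
|---|---|---|
| Bleeding at pooled rate | 1.30 × 0.122 × 0.160 = 0.03 | 1.30 × 0.122 × 0.741 = 0.12 |
| All bleed | 1.30 × 0.835 × 0.160 = 0.17 | 1.30 × 0.835 × 0.741 = 0.81 |

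With 14-day episodes all starting in Cycle 1, every episode meets an infusion day (27/27), and the all-bleed figure is 1.30 × 0.835 = 1.09.

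**The case against.** The strongest reply is that the literal reading empties the verb: an instruction to delay should mean some delay. Read with the row above, the line may mean that ublituximab resumes once the patient no longer belongs in the bleeding or Grade 4 row. The all-drugs hold and the rule favoring the more stringent recommendation both point to caution. The table is guidance, and no investigator is compelled to infuse.

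Much of this stands. It shows that a careful investigator would probably hold the drug. It does not show that the text says so. The row above is labeled by platelet grade alone, includes Grade 3 and does not mention bleeding, so returning to it is not defined by the bleeding stopping. The all-drugs hold sits beside a bullet that lets the table set the release level.

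A reader might infer that the protocol orders infusion during a bleed, or that Section 7.1 contradicts its own table. The documents support neither. The line gives an ineffective delay rather than an order to treat, and the general bullet's deference to the table makes this a tension, not a contradiction.

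**Conclusion.** The ublituximab line is wrong as written for one of the row's presentations: Grade 3 platelets with a Grade 1-2 bleed. Grade 4 platelets are handled by the row itself. Bleeds of Grade 3 or higher are handled provided they are managed under the non-hematological row. The oral-agent lines share the missing bleeding condition, but it leaves them without a delay only when baseline is already Grade 3.

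Few if any of the 27 patients are likely to be affected. That is a judgment: the documents give no rate for the triplet and no joint rate of thrombocytopenia with bleeding. The illustrative figures rest on monotherapy rates and assumed episode lengths and onset times, and do not prove that zero is the most likely count in every scenario.

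A reader might also infer a threat to the efficacy result. There is none: neither the CR definition in Section 11.2 nor the two-stage rule in Section 12.1 depends on this line. Severity is minor.

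**What to change.** In both attribution branches, extend the ublituximab release condition after the Grade 3 threshold with: *and, if present, bleeding is resolved*. Leave the rest of the line unchanged. This follows the neutropenia row and gives sites one usable criterion. Add the same condition to the row's oral-agent delay lines: the first-occurrence line in the umbralisib branch, to which the second and third occurrences refer back, and the acalabrutinib line in the other branch. The clinical team may prefer a stricter platelet grade.

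The cost is one clause in each of four lines at the next amendment, and an occasional short dosing delay, which stays subject to the 8-week maximum already in Section 7.1.

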Diarrhea Grade ≥ 3	
Provide supportive care as warranted.
 
1st occurrence:
 
 - Delay acalabrutinib and umbralisib until Grade ≤ 1; thereafter, resume both acalabrutinib and umbralisib at current dose level. 
2nd occurrence (despite supportive care):
 
 - Same as for 1st occurrence, but resume umbralisib at next lower dose level (dose reduction). 
3rd occurrence (despite supportive care):
 
 - Same as for 1st occurrence, but resume both umbralisib and acalabrutinib at next lower dose level (dose reduction for both). 
4th occurrence (despite supportive care):
 
Discontinue both acalabrutinib and umbralisib.
 
Delay ublituximab until \leq grade 2 (or until \leq grade 1 for recurrence after rechallenge); thereafter, resume ublituximab at full dose and schedule.
 
If toxicity is suspected to be related to acalabrutinib rather than umbralisib by the investigator, delay acalabrutinib until Grade ≤ 1 or baseline, thereafter, resume acalabrutinib at current dose level. For recurrences, acalabrutinib and/or umbralisib may be dose reduced.

Colitis (all Grades)	
Provide supportive care as warranted.
 
Delay umbralisib and interrupt acalabrutinib. Treat with supportive care and after resolution of colitis, resume acalabrutinib at current dose level and umbralisib at next lower dose level.
 
Upon second occurrence:
 
 - Discontinue umbralisib. - Interrupt acalabrutinib.

	
 - Treat with supportive care and after resolution of colitis, resume acalabrutinib at next lower dose level. 
Delay ublituximab until resolution to grade ≤ 1; thereafter, resume ublituximab at full dose and schedule.

Liver Toxicity (ALT/SGPT, AST/SGOT, Bilirubin, Alkaline Phosphatase)	
	
Reversible liver toxicity (transaminase elevation) has been seen on study and could be attributed to both umbralisib and acalabrutinib. Thus, any cases of grade ≥ 3 toxicity should be discussed with the study PI.

Grade 1	
Maintain current dose and schedule of acalabrutinib.
 
Maintain current umbralisib dose.
 
Assess concomitant medications and risk factors*.
 
Monitor labs every 1-2 weeks.
 
Maintain full dose and schedule of ublituximab***, if applicable.

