
Grade ≥ 3 Discuss with the study PI.
	
Monitor labs at least weekly until toxicity fully resolved (Grade 0). Once resolved:
 
 ○ Restart acalabrutinib at current dose level. ○ Restart umbralisib at 400 mg po daily. ○ Restart ublituximab*** at full dose and schedule. ○ Taper prednisone by 10 mg per week until off. 
If 2nd occurrence of liver toxicity Grade ≥ 3:
 
Discontinue umbralisib. Hold acalabrutinib and ublituximab until resolved (Grade 0). Thereafter, resume acalabrutinib at current dose level and restart ublituximab*** at full dose and schedule; however, if liver toxicity is strongly suspected to be related to acalabrutinib, treat as 3rd occurrence below.
 
If 3rd occurrence of liver toxicity to Grade ≥ 3, discontinue acalabrutinib and resume umbralisib at 400 mg po daily and ublituximab*** at full dose and schedule once toxicity resolves (to Grade 0). If toxicity does not recur, umbralisib may be escalated by one dose level after a full cycle of therapy. Re-introduction of acalabrutinib may be attempted after 3 full cycles of therapy in absence of additional liver toxicity, after discussion with the study PI. In those circumstances, acalabrutinib should be given on days 8-28 of each cycle and liver function tests (AST, ALT, bilirubin) checked within 14±7 days after the first dose of acalabrutinib, and as needed thereafter. If liver toxicity recurs to grade ≥ 3, acalabrutinib should be permanently discontinued.
 
If 4th occurrence of liver toxicity Grade ≥ 3 (while on umbralisib), permanently discontinue umbralisib. Re-introduction of acalabrutinib may be attempted after 3 full cycles of therapy in absence of additional liver toxicity, after discussion with the study PI. In those circumstances, liver function tests (AST, ALT, bilirubin) should be checked within 14±7 days after the first dose of acalabrutinib, and as needed thereafter. If liver toxicity recurs to grade ≥ 3, acalabrutinib should be permanently discontinued.

---	---

* Assess for disorders of lipids and glucose, thyroid disorders, alcohol use, viral infections, etc.

**Supportive Care – Aggressive management of lipid, glucose, other metabolic disorders, viral infections, etc.

Important: Before initiating steroids, check for viral hepatitis or CMV infection.

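### In the liver Grade ≥3 row of Table 7.1.1, a failed acalabrutinib re-introduction meets both a permanent stop and a rule allowing another re-introduction; the row's umbralisib escalation also lacks a cross-reference in the note against re-escalation

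*Combined protocol and SAP*

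**What the plan says.** All the text is in section 7.1, which introduces its rules with "General guidelines for recommended dose delays and modifications are provided below".

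**Liver Grade ≥3 row of Table 7.1.1.**
- 1st event: all three drugs are held. After resolution, umbralisib restarts at 400 mg and acalabrutinib at its current dose.
- 2nd event: umbralisib is discontinued and acalabrutinib is later resumed. If acalabrutinib is strongly suspected, the event is handled as a 3rd.
- 3rd event: acalabrutinib is discontinued and umbralisib resumes at 400 mg. Without recurrence, "umbralisib may be escalated by one dose level after a full cycle of therapy". After three full cycles free of liver toxicity, and discussion with the Study PI, acalabrutinib may be re-introduced on days 8–28. It is stopped permanently if Grade ≥3 toxicity recurs.
- 4th event, in a patient taking umbralisib: umbralisib is stopped permanently. Acalabrutinib re-introduction may again be tried, on the same three-cycle and Study PI conditions.

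The row label adds "Discuss with the study PI", and the note heading the liver section says Grade ≥3 cases "should be discussed with the study PI".

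**Notes under the dose-reduction table.** If umbralisib or acalabrutinib was reduced "due to study drug related toxicity, the dose may not be re-escalated". If the event later proves unrelated to the drug, and this is recorded, "dose re-escalation to the previous dose may be considered in consultation with the Study PI". The liver row and this note do not refer to each other.

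**The concern.** The main point is the overlap at the 4th event. A patient whose re-introduction of acalabrutinib has just failed falls under a sentence that ends the drug permanently and under another that lets it be tried again. The liver section notes that reversible transaminase rises have already been seen on study and could come from either oral drug. Section 12.4.2 counts Grade ≥4 AST or ALT elevations and Grade ≥3 bilirubin elevations, if at least possibly related, among the events that can halt accrual. Whether a patient may be rechallenged a second time should therefore be unambiguous at all four sites.

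The secondary point is that the row permits an upward umbralisib step that the general note, read alone, does not, and the note's own exception is framed differently from the row.

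**Working it through.** No power, alpha or sample-size figure is involved. The check traces the rules and compares the sentences.

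**Inputs.** The liver Grade ≥3 row and the notes in section 7.1; umbralisib dose levels 800, 600 and 400 mg from the dose-reduction table; umbralisib on days 1–7 of each 28-day cycle after cycle 1 (section 5.3); maximum accrual 27 (section 12.3).

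**Main point: default path for a patient starting at full dose.**

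| Grade ≥3 liver event | Drugs in the regimen at the event | Instruction |
|---|---|---|
| 1st | umbralisib 800 mg, acalabrutinib | umbralisib to 400 mg, acalabrutinib resumed |
| 2nd | umbralisib 400 mg, acalabrutinib | umbralisib off, acalabrutinib resumed |
| 3rd | acalabrutinib, no umbralisib | acalabrutinib off, umbralisib 400 mg, then possibly 600 mg |
| 4th, after re-introduction | umbralisib days 1–7, acalabrutinib days 8–28 | two rules apply |

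The two rules at the 4th event are:
- End of the 3rd-occurrence rule: acalabrutinib stops permanently. Nothing is said about umbralisib.
- 4th-occurrence rule: umbralisib stops permanently. Acalabrutinib may be re-introduced.

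Earliest re-introduction: 3 cycles × 28 days = 84 days of therapy. Events needed on the ordinary count: 4.

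On the shortcut path (2nd event handled as a 3rd), a failed re-introduction is numerically the 3rd event. The table does not say how to number it. Only on the assumption that it becomes the 4th would three events reach the overlap.

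**Secondary point: escalation.** The escalation sentence is reached after 3 events, or 2 by the shortcut, plus one cycle (28 days) without recurrence.

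| Sentence followed | Condition | Umbralisib dose | Per 7-day course |
|---|---|---|---|
| Note: bar on re-escalation | reduced for drug-related toxicity | 400 mg | 7 × 400 = 2,800 mg |
| Liver row | no recurrence for a full cycle | 600 mg | 7 × 600 = 4,200 mg |
| Note: exception, previous dose 800 mg | event found unrelated, recorded | 800 mg | 7 × 800 = 5,600 mg |
| Note: exception, previous dose 600 mg | event found unrelated, recorded | 600 mg | 7 × 600 = 4,200 mg |

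The row and the exception therefore differ in trigger, and in target for a patient cut straight from 800 to 400 mg. Section 7.1 states no general order of precedence between table and notes. Its one tie-break, "In case of concurrent toxicities, follow the more stringent dose modification recommendations", covers concurrent toxicities, which this is not.

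**The case against.** **On the overlap.** The 4th-occurrence rule speaks of re-introducing acalabrutinib, which presupposes that it is off. It also omits the days 8–28 schedule that the 3rd-occurrence rule uses to separate the two oral drugs. Both features fit an event on umbralisib before acalabrutinib has returned. The commands are unequal: one is a permanent stop, the other an option needing Study PI discussion, so a site could comply with both by stopping both drugs. The overlap also depends on reading the reference to being on umbralisib at regimen level. Liver tests 14 ± 7 days after a day 8 first dose fall on days 15–29, almost wholly outside umbralisib days 1–7. This shows the likely intent, and it stands. It does not remove the literal overlap, because the text does not limit the 4th-occurrence rule to the period before re-introduction.

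**On the escalation.** A reader might infer that the row flatly contradicts the note, or that a site cannot tell whether 600 mg is allowed. The documents do not support that. On the default path the 3rd event occurs off umbralisib; on the shortcut path acalabrutinib is strongly suspected. Acalabrutinib is then stopped, and umbralisib must be tolerated for a full cycle. The row is specific to this toxicity and calls for Study PI discussion, so it plainly governs, and the note's exception covers much of the case. Going to 600 rather than 800 mg is also the more cautious choice. What remains is a missing cross-reference: the row does not ask for the recorded unrelatedness finding on which the exception depends.

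**Conclusion.** The main point holds on the literal text for the default path: one sentence permits a further acalabrutinib rechallenge that another forbids. It rests on the ordinary event count and on reading umbralisib use at regimen level. A reader might infer that the plan intends a second rechallenge after a failed one. The wording does not support that; the likelier intent is that the permanent stop governs. The secondary point holds only as a missing cross-reference.

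This is a minor dosing-safety correction. The overlap takes four Grade ≥3 liver events in one patient among at most 27. The documents give no frequency for these branches; that they are rare is an inference from how many events they require. The rules are recommended guidelines applied with Study PI discussion. Nothing here touches the complete-response analysis, the error rates or the sample size.

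**What to change.** Make two wording changes in section 7.1.

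1. **Table 7.1.1, liver Grade ≥3, 4th occurrence.** Keep the permanent umbralisib stop. To the sentence allowing acalabrutinib re-introduction after three full cycles, add: *unless acalabrutinib was already re-introduced after the 3rd occurrence, in which case it is permanently discontinued*.
2. **Note against re-escalation.** Add: *except as specified for liver toxicity Grade ≥3 in Table 7.1.1, in consultation with the Study PI*.

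The first change should qualify only the re-introduction sentence. Restricting the whole 4th-occurrence rule to events before re-introduction would delete the umbralisib stop that the text now literally imposes after a failed re-introduction, and would leave no umbralisib instruction for that event.

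The second change lets the row's own trigger stand. If the sponsor wants an attribution finding recorded before the step to 600 mg, that is a clinical choice and should be written into the row.

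The cost is one clause in a table row and one in a note. Design, sample size and analysis do not change.
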